The design for this study is an observational cohort study utilizing prospectively collected electronic medical record (EMR) data from usual clinical care at AHF Midtown Manhattan Healthcare Center, obtained from the OPERA® Observational Database.

The study population will consist of adults vaccinated against SARS-CoV-2 virus receiving the Roche SARS-CoV-2 Semi-Quant Spike Ig AB test as part of their usual clinical care. These individuals will be followed from vaccination until study end.

EXPOSURES OF INTEREST

Initial vaccination with Pfizer, Moderna, and J&J COVID vaccines, booster vaccination with Pfizer, Moderna, and J&J vaccines, and concordant boosting versus discordant boosting

SUBGROUPS OF INTEREST

HIV-positive versus HIV-negative patients, individuals with at least 2 measurements of antibody levels, and boosted individuals are the subgroups of interest.

STUDY ENDPOINTS

Endpoints for both the primary and secondary objectives are non-responders and low responders and rates of decline of SARS-CoV-2 antibodies

- Non-response will be defined as: 0 to <50 U/mL
- Low response will be defined as: ≥ 51 to ≤ 250 U/mL
- Adequate response will be defined as: >251 U/mL

Roche's Elecsys semi-quantitative spike Ab Ig assay is a commercially available assay that can potentially be utilized to help guide the need for an additional vaccination dose based upon the levels of antibodies that have been previously clinically correlated with neutralizing antibodies. As part of routine care, Ab Ig assays were performed for some patients at the AHF Midtown Manhattan Healthcare Center and results were recorded in their EHR.

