To normalize across different neutralization assays utilized in phase 3 studies of various COVID-19 vaccines, Khoury, et al., estimated that a 50% protective neutralization level equivalent to 20% of the mean titer in the convalescent subjects equates to a measured in vitro neutralization titer of between 1:10 and 1:30 was approximated at 54 international units IU/ml (95% CI 30–96 IU/ml) against wild-type CoV-19 infection.^{xx} During the period of COVID-19 infection where the Delta virus predominated, a quantitative spike Ab's >250 IU/mL was deemed adequate, based on studies that show that an antibody titer of 4-6x wild-type SARS-CoV-2 were required to effectively neutralize Delta viral strains.^{xxi,xxii, xxiii} We thus utilized a threshold level of >250 (5x wild-type ab levels) IU/mL as an adequate vaccine response against circulating Delta virus post last vaccination recommended in a series, a level of <50 IU/mL as a non-responsive post vaccination titer (inadequate for even wild-type Co-V-2 infection), and levels between (50-250 IU/mL) as a low vaccine response. Non and low-responders who had Co-V-2 Spike Ig levels that were inadequate based on the correlation of Spike Ig levels and neutralizing ab correlations relative to the predominant circulating viral strains were offered optional booster vaccinations with subsequent antibody response measurement post vaccination as standard of care. These recommendations are the current one's implemented during the Delta Co-V-2 19 outbreak by the Ministry of Solidarity and Health of France and the COVID Guidelines group in Geneva, where 260 IU/mL and 300 IU/mL, respectively, are considered gray zones of antibody protection against the Delta virus and where booster vaccinations are recommended for consideration.^{xxiv, xxv}

STUDY COVARIATES

Covariates of interest include: age, sex, race, ethnicity, HIV status, region, payer, immunosuppressive conditions, CD4 cell count, comorbid conditions, BMI. This information will be obtained from each patient's electronic health records.

7. Statistical Analysis

ANALYSIS OF DEMOGRAPHICS/BASELINE CHARACTERISTICS

Demographic and clinical characteristics will be summarized in the overall population using medians with interquartile ranges (IQR) for continuous variables and frequencies with proportions for categorical variables.

ANALYSIS OF PRIMARY OBJECTIVES

Objective #1: COVID-19 vaccine non-response and low response as measured by antibody test by HIV status

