Records will be examined retrospectively to determine which patients, both HIV-positive and negative, were non-responders, or who developed low or adequate quantitative Ig spike antibodies using the Roche Elecsys semi-quantitative spike Ab Ig assay during usual clinical care.

Demographic and clinical characteristics will be summarized by vaccine response level using medians with interquartile ranges (IQR) for continuous variables and frequencies with proportions for categorical variables. Statistical comparisons between vaccine response level will be performed using Pearson's chi-square or Fisher exact tests for categorical variables and Wilcoxon rank-sum test for continuous variables, using an adequate response as the comparator.

Incidence rates and 95% confidence intervals of COVID vaccine adequate response, non-response and low response to COVID vaccines will be estimated using univariate Poisson regression. Incidence rates will be obtained both overall and by vaccine type. The incidence rate is defined as the number of events during follow-up divided by person-time at risk of the event. Estimating incidence rates with Poisson regression allows the use of all person-time time at risk of the outcome, even with differential lengths of follow-up between groups.

Objective #2: Rate of decline in antibody levels over time by HIV status, vaccine type, and baseline CD4 count after initial vaccination

Rates and 95% confidence intervals of antibody levels decay will be estimated among individuals with at least two antibody measurements. Univariate linear regression, will be employed, using the continuous antibody level as the dependent variable, and timing of tests as

the dependent variable. Robust variance estimator will be used to account for repeated measures. Rates of decay will be produced overall, and stratified by HIV status, vaccine type and baseline CD4 cell count.

ANALYSIS OF SECONDARY OBJECTIVES

Objective #3: COVID-19 boosters given

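### Objective #2 estimates decay by pooled regression in retested patients, although a low titre led to a booster offer and no rule drops post-booster values: the slope is biased in a direction the documents do not fix

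*Combined protocol and SAP*

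**What the plan says.** Section 7, Objective #2 (a primary objective), sets the analysis population: "Rates and 95% confidence intervals of antibody levels decay will be estimated among individuals with at least two antibody measurements". The method is "Univariate linear regression, will be employed, using the continuous antibody level as the dependent variable", with test timing as the other variable. The model has no patient effect and no covariates, and no log transformation is mentioned. The one allowance for several tests per patient is "Robust variance estimator will be used to account for repeated measures". Results are given overall and by HIV status, vaccine type and baseline CD4 count.

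Section 6 describes how the tests arose. There was no schedule: "As part of routine care, Ab Ig assays were performed for some patients at the AHF Midtown Manhattan Healthcare Center". On the cut-off: "We thus utilized a threshold level of >250 (5x wild-type ab levels) IU/mL as an adequate vaccine response". Patients below it "were offered optional booster vaccinations with subsequent antibody response measurement post vaccination as standard of care". On follow-up: "These individuals will be followed from vaccination until study end".

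The Objective #2 heading reads "Rate of decline in antibody levels over time by HIV status, vaccine type, and baseline CD4 count after initial vaccination". That implies that values after a booster do not belong, but no sentence says so. The Sensitivity Analyses entry in Section 7 is NA.

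**The concern.** Two features act together.

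- **Selection.** A patient with a low first titre who accepts a booster has no later pre-booster test. Requiring two tests therefore conditions partly on the first titre. A pooled regression also takes its slope from comparisons between patients tested early and patients tested late, so this selection enters the slope directly. A robust variance changes the standard error and leaves the estimate as it is.
- **No stop at booster.** If a boosted low responder's second value enters Objective #2, a rise caused by the booster is read as part of the decline after primary vaccination.

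The decay rate is a primary result, and the Synopsis links antibody measurement to the timing of boosters. The strata are exposed as well: if HIV, vaccine or CD4 groups differ in the share of titres at or below 250, they are selected to different degrees and the contrasts between their slopes can be distorted. No planned analysis would reveal any of this.

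**Working it through.** The documents give no slope, variance, retest rate or number boosted, so there is no plan figure to reproduce. The mechanism was checked by simulation. Only the 250 cut comes from the documents; every other input is an assumption.

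**Why the direction depends on scale.** Suppose only first titres above 250 lead to a second pre-booster test. A patient first tested late must have started higher to be above 250 then. Among retested patients, later test times therefore go with higher starting levels, which flattens a pooled log slope. On the raw scale the loss in U/mL per day is proportional to the level, so keeping the high-titre patients raises the absolute slope.

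**Setting A.**
- Half-life 70 days, so the true slope is −log10(2)/70 = −0.3010/70 = −0.0043 log10 per day.
- Geometric mean 1000 at day 21 (also 2000); between-person SD 0.45 and within-person SD 0.1, 0.2 or 0.3, all log10.
- First test on days 21–180, second test 60–120 days later, retest probability 0.6 above 250.
- With a mean of 1000 at day 21, the expected level at day 180 is 1000 × 2^(−159/70) = 207, below the cut. Late first tests are therefore selected hard.

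Ratio of the planned pooled slope (two or more tests, post-booster values excluded) to the slope if everyone were retested unboosted:

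| Geometric mean at day 21 | Retest probability, low / high titre | Log scale | Raw scale |
|---|---|---|---|
| 1000 | 0 / 0.6 | 0.79, 0.84, 0.90 | 1.14 to 1.22 |
| 1000 | 0.3 / 0.6 | 0.94, 0.96, 0.98 | 1.08 to 1.10 |
| 2000 | 0 / 0.6 | inside the range above | 1.04 to 1.07 |
| 2000 | 0.3 / 0.6 | inside the range above | about 1.03 |

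Overall this is about 2–21% too shallow on the log scale and 3–22% too steep on the raw scale. Repeat runs differ by about one percentage point on the raw scale.

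**Post-booster values left in.** With 60% of low titres boosted and re-measured, a 20-fold rise, and the unboosted retested at the same rate whatever their titre, 37–71% of the log slope and 45–87% of the raw slope remain.

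**Setting B.** Half-life 90 days (true slope −ln(2)/90 × 30 = −0.231 natural-log units per 30 days), median 800 at time 0, SDs 1.2 and 0.3 on the natural-log scale, first test on days 21–150, second 40–120 days later, 40% of unboosted patients retested except where stated. The raw slope with everyone retested is about −155 U/mL per 30 days.

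| Scenario | Log slope | Raw slope |
|---|---|---|
| Retesting unrelated to titre, no boosting | −0.230 | −152 |
| 60% of low titres boosted, post-booster excluded | −0.216 | −178 (178/154 = 1.15) |
| 100% boosted, post-booster excluded | −0.191 | −194 (194/156 = 1.24) |
| 60% boosted, post-booster included | +0.027 | −15 |
| No boosting, low titres retested more (80% v 20%) | −0.210 | −94 (94/154 = 0.61) |

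The first row is the control: without titre-dependent selection the planned estimator shows essentially no bias.

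**Does the remedy work?** In Setting B, with 60% and 100% of low titres boosted, a random-intercept model on all pre-booster log titres, including patients with one test, gives −0.230 and −0.232. Limited to two or more tests it gives −0.235 and −0.242. Pooled regression in a companion run gives −0.212 and −0.188. In Setting A the mixed model on all patients recovers 100% of the slope in every case, against 100–111% when limited to two or more tests.

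**The case against.** The strongest reply has four parts.

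1. *The aim is descriptive and the subgroup is declared.* Section 3 says the rate of decline will be described, and Section 6 lists patients with at least two measurements as a subgroup of interest. This stands as a reason to keep that analysis. It does not make a pooled slope in that subgroup the decay rate of vaccinated patients.
2. *Post-booster values are excluded by implication.* The heading says so in effect, and Objective #4 handles decline after a booster. That is a fair reading, and the documents do not show that the sponsor intends to include such values. But follow-up runs to study end and no data rule exists, so a programmer could include them without breaching the plan.
3. *The link between titre and retesting is partly inferred.* This stands. The documents make it only through an optional booster; how unboosted patients came to be retested is not stated. If few titres are low, or many low responders decline the booster and are retested, the bias is a few percent.
4. *Most of the log-scale bias comes from pooling, not from the two-test rule.* This also stands: a mixed model limited to retested patients is much closer to the truth. The restriction still adds some bias of its own and discards usable data.

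A reader might infer that decay will look slower than it is. The documents do not support that. It holds on the log scale under the assumed selection, but the plan states the untransformed level, on which the same selection makes the slope too steep. Over-retesting of low responders, or retained post-booster values, makes the raw slope too shallow.

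**Conclusion.** The concern holds as a bias of undetermined direction and size. The documents establish the two-test restriction, pooled regression with only a robust variance, a booster offer and re-measurement following a low titre, no test schedule, no stated exclusion of post-booster values and no sensitivity analysis. The percentages rest on assumed titre distributions, decay and retest rates, and illustrate plausible size only. With post-booster values excluded, the error runs from a few percent to about a fifth in Setting A, and up to about 24% on the raw scale in Setting B. The missing rule on post-booster values is the larger exposure: much of the decline can disappear, and in Setting B nearly all of it. This should be corrected before analysis, because the decay rate is a primary result.

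**What to change.** For Objective #2:

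- State that only tests after full vaccination and before any booster are used.
- Include every eligible patient with such a test, also those with only one.
- Fit a linear mixed model of log titre on time since full vaccination, with a random intercept and a random slope if the data support it. Report the slope and half-life overall and by the planned strata.
- Tabulate single-test against retested patients: first titre, time of first test, HIV status, vaccine type and CD4 count.
- Keep the two-or-more-test regression as a sensitivity analysis, also restricted to pre-booster values.

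The cost is SAP wording, a standard model and one table; no new data are needed. There are two limits. The model assumes that retesting and boosting are explained by recorded titres and covariates, which cannot be verified from these data. The result is a proportional decay rate, not a loss in U/mL per unit of time, so the text of the objective should say which is meant.

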“Should COVID-19 Quantitative Antibody Titers be Implemented to Guide COVID-19 Booster Vaccinations Regardless of HIV status, Immunosuppression, or Age?”

**Study Protocol
Version 2.5**

.....

Prepared by:

[name], [name], and [name]

October 29, 2021

Table of Contents

Contents

1. SYNOPSIS	3
2. INTRODUCTION	4
BACKGROUND	4
RATIONALE FOR THE STUDY	6
3. RESEARCH OBJECTIVES	7
PRIMARY OBJECTIVE(S)	7
SECONDARY OBJECTIVE(S)	7
4. DATA SOURCE	8
AHF MIDTOWN MANHATTAN HEALTHCARE CENTER	8
DESCRIPTION OF THE DATABASE AND PREPARATION OF ANALYTICAL FILES	8
5. STUDY POPULATION	11
INCLUSION CRITERIA	11
EXCLUSION CRITERIA	11
6. STUDY DESIGN	12
OVERVIEW OF STUDY DESIGN	12
EXPOSURES OF INTEREST	12
SUBGROUPS OF INTEREST	12
STUDY ENDPOINTS	12
STUDY COVARIATES	13
7. STATISTICAL ANALYSIS	14
ANALYSIS OF DEMOGRAPHICS/BASELINE CHARACTERISTICS	14
ANALYSIS OF PRIMARY OBJECTIVES	14
ANALYSIS OF SECONDARY OBJECTIVES	15
SENSITIVITY ANALYSES	15
SUBGROUP ANALYSES	16
8. STUDY CONDUCT	17
REGULATORY AND ETHICAL CONSIDERATIONS	17
INFORMED CONSENT	17
DATA PRIVACY & PERSONALLY IDENTIFIABLE INFORMATION (PII)	17
ADVERSE EVENT REPORTING	17
9. ADMINISTRATIVE MATTERS	18
QUALITY ASSURANCE	18
10. REFERENCES	19

1. Synopsis

Little real-world data are available on the antibody response after COVID-19 vaccination in HIV-negative and HIV-positive individuals, the potential usage of quantitative antibody testing to determine those at greatest risk for infection while helping guide additional vaccination timing, and the antibody response of vaccine boosting in individuals with no response or low response to initial vaccinations. At the moment, clinicians must rely on general category recommendations and clinical judgement when advising their patients on the utility of vaccine boosting, as well as their level of protection from COVID vaccination. Real-world evidence is needed to better inform such decisions. The aim of this study is to assess levels of COVID-19 vaccine response through measuring surrogate Ig spike antibody measurements, to determine the rates of antibody level decay after vaccination, and to measure the efficacy of utilizing these antibody measurements to help guide the timing of booster doses among HIV-negative and HIV-positive patients.

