Additional vaccine doses may be particularly important for healthcare providers who are often in direct contact or close proximity to SARS-CoV-2 infected individuals, where resurgences of SARS-CoV-2 infection have been reported across the U.S., especially in the era of the SARS-CoV-2 Delta strain.^{iv,v} In addition, the odds of long COVID-19 symptomology were estimated in one study to be 50% less in the vaccinated versus the insufficiently immunized population.^{vi} In contrast, those healthcare workers who have sufficient immunogenicity against prevalent SARS-CoV-2 strains, may not fit the compartmentalization into time-based vaccination strategies, but rather individualized immunologic responses to vaccinations. Furthermore, due to the

interpersonal variability of immunologic response, differences in the attenuation of individual antibody levels, and the complexity added by the availability of different vaccines, dosing regimens, and decay rates, a better methodology for determining when a specific individual requires re-vaccination should be determined. With no current correlations of protection, especially in populations in which preventing infection is the goal, the higher the antibody titer the better. Studies have demonstrated that those who were vaccinated for SARS-CoV-2 are generally in favor for receiving additional booster doses. Furthermore, an increase in significant adverse events, other than lymphadenopathy, have not been reported in recipients of additional SARS-CoV-2 vaccine doses beyond the primary series.^{vii} The effectiveness of additional booster vaccination over the primary vaccination series in preventing re-infection with SARS-CoV-2 for currently available vaccine types have been demonstrated in a number of studies^{viii,ix}, only the timing of when and to whom to give booster dosing remains in debate. Lastly, multiple studies illustrate that the maximizing of timing between vaccination doses, regardless of mRNA or adenovirus vaccination type, results in improved immunologic responses both in initial degree, but also in the persistence of response.^{x,xi,xii,xiii}

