Limited real-world data are available on the antibody response after COVID-19 vaccination comparing HIV-negative and HIV-positive individuals. There are also limited information that would allow the potential usage of quantitative antibody testing to determine those at greatest risk for infection while could help in guiding the timing of additional vaccinations. There are also limited information on the antibody response of vaccine boosting in individuals, especially those with altered immune response that might lead to no response or low response to the primary vaccination series. At the moment, clinicians must rely on clinical judgement when advising their patients on the utility of vaccine boosting, as well as their level of protection from COVID vaccination. Additional information would be helpful in informing decisions on third doses in different populations such as HIV positive people, whose responses to COVID-19 vaccine and immune status would help define the timing and need for an additional vaccination based on current recommendations. Real-world evidence is needed to better inform such decisions.

3. Research Objectives

PRIMARY OBJECTIVE(S)

Objective #1: Describe COVID-19 vaccine response including frequency of non-response, low response, and adequate response as measured by antibody test by HIV status (e.g., rates, and relationship to demographic and clinical characteristics, as well as vaccine types)

Objective #2: Describe rate of decline in antibody levels over time by HIV status, vaccine type, and baseline CD4 count after initial vaccination as well as other parameters.

SECONDARY OBJECTIVE(S)

Objective #3: Describe response to COVID-19 boosters given (vaccine types, concordant vs. discordant boosters, duration from initial vaccine completion, antibody response, and side effects)

Objective #4: Describe rate of decline in antibody levels over time by HIV status, baseline CD4 count, by vaccine given, and after booster vaccination

Objective #5: Recording breakthrough infections after vaccinations and assessing antibody levels pre-breakthrough infection

4. Data Source

AHF MIDTOWN MANHATTAN HEALTHCARE CENTER

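### The planned decay rates are slopes of the raw antibody level, so if decay is roughly proportional they mix starting level with persistence and are not comparable across strata that start at different levels

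*Combined protocol and SAP*

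**What the plan says.** Section 7, Objective 2 (primary), defines the analysis set: "Rates and 95% confidence intervals of antibody levels decay will be estimated among individuals with at least two antibody measurements". The model is given as "Univariate linear regression, will be employed, using the continuous antibody level as the dependent variable", with test time as the other variable. The text labels time a dependent variable as well, an evident slip for independent. Correlation within a patient is handled in one sentence: "Robust variance estimator will be used to account for repeated measures". The output is then defined: "Rates of decay will be produced overall, and stratified by HIV status, vaccine type and baseline CD4 cell count".

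Objective 4 uses the same model, with booster type in place of vaccine type. Its analysis set needs two measurements, of which only one has to follow the booster. The Synopsis repeats the linear model for both objectives and gives as part of the study's aim "to determine the rates of antibody level decay after vaccination".

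The documents mention no log scale, half-life, percent decline, adjustment for starting level or non-linear time term. The Sensitivity Analyses entry is NA. No expected starting level, decay rate or sample size is stated.

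**The concern.** Section 3 sets Objective 2 as: "Describe rate of decline in antibody levels over time by HIV status, vaccine type, and baseline CD4 count after initial vaccination". The Background names "interpersonal variability of immunologic response, differences in the attenuation of individual antibody levels" as separate sources of variation, that is, how strongly a person responds and how fast the response fades. Objective 1 covers the first and Objective 2 should cover the second.

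A straight line on the untransformed level gives U/mL lost per unit time. If the loss is roughly proportional to the level, that slope is the proportional decay rate multiplied by the level from which the group starts. Objective 2 would then partly report Objective 1 again. A stratum with a weaker initial response would show a shallower slope, which a reader could take for better persistence. The robust variance adjusts the standard errors for repeated tests and does not change what the slope estimates.

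**Working it through.** **Inputs.** The outcome scale, the regressor and the strata come from Section 7. The decay form, half-lives (60 to 120 days), starting levels and test days below are assumptions, because the documents give none. The plan states no figure that could be reproduced, so the check is of the estimator itself.

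**1. Same persistence, different starts.** Let the level be y(t) = A × 2^(-(t-21)/h), with A the level at day 21 and h the half-life in days. With tests at days 30 and 180:

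slope = A × [2^(-159/h) - 2^(-9/h)] / 150

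For h = 90 the bracket is 0.2939 - 0.9330 = -0.6391.

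- A = 2000: 2000 × (-0.6391) / 150 = -8.5 U/mL per day
- A = 500: 500 × (-0.6391) / 150 = -2.1 U/mL per day

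A factors out, so the ratio is 2000/500 = 4 at any half-life. The 4 is the assumed start ratio returned. It shows the mechanism and does not estimate how large the effect will be in this cohort.

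**2. Same start, different persistence.** Least-squares slope in U/mL per 30 days, tests spread evenly from day 21 to the last day, A = 2500:

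| Last test day | h = 60 | h = 120 | Ratio |
|---|---|---|---|
| 120 | -505.3 | -328.2 | 1.54 |
| 180 | -375.9 | -279.5 | 1.34 |
| 240 | -286.0 | -239.5 | 1.19 |

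A true 2-fold difference in half-life moves the raw slope only about 1.2- to 1.5-fold. A start difference of that size in the opposite direction cancels it.

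**3. The order can reverse.** With tests to day 180, a group starting at 2500 with h = 120 has slope -279.5. A group starting at 1250 with h = 60 has slope -188.0. The group with half the half-life shows the slower decline.

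**4. Log scale.** log2 y = log2 A - (t-21)/h, so the slope per 30 days is -30/h: -0.500, -0.333 and -0.250 for h = 60, 90 and 120, whatever A is. At h = 90 this is 2^(-0.333) - 1, about -21% per 30 days.

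A simulation agrees. It had 200 patients per group, two tests each, between-person log-SD 1.0, measurement log-SD 0.15, h = 90 in both groups and a 2-fold difference in start. Mean raw slopes were about -187 and -94 U/mL per 30 days; mean log2 slopes were -0.332 and -0.333.

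**5. Objective 4.** Its eligibility rule admits a patient with one test before and one after the booster. The slope through that pair measures the rise produced by the booster. Taking logs does not turn it into post-booster decay.

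**The case against.** Several points on the other side are sound.

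- **The objectives are descriptive.** They set out to describe, and no test of slopes between strata is planned. U/mL lost per unit time is a legitimate description where the response categories are absolute cut-offs. This stands, but rates with confidence intervals tabulated by stratum will be read side by side, and a rate of decay will be read as persistence.
- **The documents do not establish the premises.** They neither state that decay is proportional nor give starting levels by HIV status, CD4 or vaccine. The fold language in the Background and Study Endpoints concerns neutralisation thresholds for wild-type and Delta virus, not decline over time. This stands, and the point is therefore conditional.
- **The raw slope is not empty.** A reader might infer that it mainly reflects starting level or allows no comparison at all. That goes too far. With equal starts, the two-test set-up above gives about -9.9, -8.5 and -7.3 U/mL per day at half-lives of 60, 90 and 120 days for A = 2000, so persistence is still ranked, though weakly. Over longer windows the ranking can fail: with tests to day 240 and a start of 250, the slope per 30 days is -27.5 at h = 40 and -28.6 at h = 60.
- **Extrapolation is not planned.** A reader might also infer that the study will mispredict when a patient reaches 250 U/mL, or report negative levels. No such prediction is among the planned outputs, and booster offers are tied to the measured level rather than to a slope.
- **A log model has its own weakness.** The non-response category begins at 0 U/mL, so a substitution rule is needed, and it matters most for the lowest responders.

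**Conclusion.** The concern holds in conditional form. If decay is roughly proportional, the planned rate equals persistence scaled by starting level. It is then not a measure of persistence that can be compared across HIV status, vaccine or CD4 strata whose starting levels differ. Over the assumed half-lives and test windows, a start difference of about 1.2- to 1.5-fold is enough to offset a 2-fold difference in half-life, and a larger one reverses the order. How far this happens here depends on starting levels that the documents do not give. The raw slope stays valid as average absolute change. Separately, the Objective 4 analysis set can include pairs of tests that do not measure decay, whichever scale is used. Because a log-scale analysis uses the same data and serves the stated objective better, this is a worthwhile, inexpensive improvement to a primary analysis; it does not invalidate the study.

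**What to change.** - **Objectives 2 and 4, and the Synopsis:** make the decay analysis a regression of log antibody level on time since the last dose, keeping the robust variance by patient. Report percent change per month or half-life with 95% CI, overall and by stratum. Correct the label on time to independent variable.
- **Zero and assay-limit results:** fix one substitution value in advance.
- **Raw U/mL slope:** keep it as a supplementary description of absolute change.
- **Objective 4:** fit decay only to post-booster measurements, in patients with at least two of them. Describe the change from before to after the booster under Objective 3.

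The cost is a short change to the text, with no new data. The downsides are a less familiar scale, some dependence on the substitution value for the lowest results, and fewer patients in Objective 4.
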